3.4.3. Individual Stopping Rules

If an individual subject develops any of the following, the subject will not receive a second dose of IP in Part B. Subjects in Part B (MAD cohort) who meet these criteria and who have received the first dose of IP will remain in the study and continue to be followed per the [Schedule of Activities](#):

- Laboratory values meeting criteria for potential drug induced liver injury (see [Section 8.4.2](#)).
- Illness or clinical adverse event that prevents daily activity and requires medical intervention (ie CTCAE v4.0 Grade 3).
- Any serious adverse event (irrespective of relatedness to study drug).
- Any infection requiring the use of oral or parenteral antibiotics between first and second dosing of IP requires approval by sponsor clinician or medical monitor prior to subject receiving a second dose of IP.
- Increase in SLE or RA disease activity requiring use of prohibited medications (See [Appendix 2](#)), OR doses or formulations of medications inconsistent with those allowed (See [Appendix 3](#)).
- Prior CTCAE v4.0 Grade 4 infusion reaction during first infusion.

The following criteria will not be considered as Individual Stopping Rules (due to the anticipated effects of PF-06835375 on blood counts):

- Lymphopenia: CTCAE v4.0 Grade 2 lasting 14 days or less OR Grade 3 lymphopenia lasting 7 days or less. For subjects with abnormalities present on Day 1 prior to dose (ie, CTCAE v4.0 Grade 1 or 2), a two-grade shift lasting 14 days or less.
- Neutropenia: CTCAE v4.0 Grade 2 lasting 7 days or less OR Grade 3 lasting 3 days or less.
- Thrombocytopenia: CTCAE v4.0 Grade 2 lasting 7 days or less OR Grade 3 lasting 3 days or less.

3.5. Criteria for End of Study

All subjects will be followed through the Week 16 visit. In order for the Week 16 visit to be the subject's last clinic study visit, B cell counts meet at least one of these criteria:

- B cell count is \geq 50% of baseline value AND is stable or increasing between Week 12 and Week 16 measurements, OR
- B cell count is \geq lower limits of normal (defined as 80 cells/ μ l¹⁹) at Week 16.

If at least one of the above criteria are not met at Week 16, subjects will continue in the study and will be followed until B cell count meets at least one of these criteria:

- B cell count is \geq 50% of baseline value AND is stable or increasing between the two measurements at least two weeks apart, OR
- B cell count is \geq lower limits of normal (defined as 80 cells/ μ l¹⁹), OR
- B cell count reaches a new stable (or increasing) detectable level AND subject is clinically stable for minimum of two consecutive visits, each at least two weeks apart, based on the assessment by both the sponsor AND the investigator. The earliest B cell count that can be considered for this criterion is from the Week 20 visit. As a result, subjects will not be discharged prior to availability of Week 24 lab results for B cells under this criterion.

B-cell counts obtained from CLIA certified central lab will be used for this determination.

Baseline value is defined as the average of Screening and Day 1 pre-dose values. In cases where only one value (ie, screening or Day 1 pre-dose) is available, this one value will be used as the baseline. Stable is defined as ± 5 cell/ μ l. Values obtained by the central lab will be used.

B cell counts data will be available only after subject completes the clinic visit due to the required shipment of samples to central lab and their processing time. Once subject meets the criteria for the end of study described above, a phone visit will take place within approximately 1-2 weeks, prior to the next scheduled in clinic visit. This phone visit will be considered the end of study visit/last visit.

Subjects may be asked to return for additional follow up visits beyond the anticipated end of study visit for safety reasons as determined by the Investigator in consultation with the sponsor medical monitor.

4. SUBJECT ELIGIBILITY CRITERIA

This study can fulfill its objectives only if appropriate subjects are enrolled. The following eligibility criteria are designed to select subjects for whom participation in the study is considered appropriate. All relevant medical and nonmedical conditions should be taken into consideration when deciding whether a particular subject is suitable for this protocol.

Subject eligibility should be reviewed and documented by an appropriate member of the investigator's study team before subjects are included in the study.

4.1. Inclusion Criteria

Subjects must meet all of the following inclusion criteria to be eligible for enrollment into the study:

1. Evidence of a personally signed and dated informed consent document indicating that the subject has been informed of all pertinent aspects of the study.
2. Willing and able to comply with scheduled visits, treatment plan, laboratory tests and other study procedures.
3. Male or female subjects between the ages of 18 and 70 years (inclusive) at the time of Screening visit.
4. Subjects who are, in the opinion of the investigator, sexually active and at risk for pregnancy with their partner(s) must agree to use one highly effective form of contraception as outlined in this protocol for the duration of the study and for at least three months after the last dose of investigational product. In addition, based on contraception use recommendations from other similar agents that deplete B-cells, the sponsor strongly recommends that all subjects use highly effective contraception for a minimum of 6 months following the last dose of IP. This time frame of 6 months after the last dose of IP is strongly recommended but not required. Male subjects who are sexually active must agree to use a condom to prevent potential transmission of investigational product in seminal fluid starting for the same duration.

Female subjects of non-childbearing potential must meet at least 1 of the following criteria:

- a. Achieved postmenopausal status, defined as follows: cessation of regular menses for at least 12 consecutive months with no alternative pathological or physiological cause and have a serum follicle-stimulating hormone (FSH) level confirming the postmenopausal state; If post-menopausal for ≥ 5 years, it is at the investigator's discretion whether to confirm post-menopausal status by FSH.
- b. Have undergone a documented hysterectomy and/or bilateral oophorectomy.
- c. Have medically confirmed ovarian failure.

All other female subjects (including female subjects with tubal ligations) are considered to be of childbearing potential.

5. For females of childbearing potential, two negative pregnancy tests (one negative serum pregnancy test at Screening and one negative urine pregnancy test on Day 1) are required before receiving the investigational product.
6. Body Mass Index (BMI) of 17.5 to 40 kg/m² AND total body weight > 45 kg.
7. Subjects must meet diagnostic criteria either for Rheumatoid Arthritis or Systemic Lupus Erythematosus below:
 - a. ***Rheumatoid Arthritis criteria:***
 - Confirmed diagnosis of Rheumatoid Arthritis according to the 2010 American College of Rheumatology (ACR)/European League Against Rheumatism (EULAR) criteria (See [Appendix 6](#)) at Screening, with symptom duration at least 6 months prior to Screening visit.
 - Positive with Rheumatoid Factor and/or anti-citrullinated peptide antibody (ACPA) at Screening.
 - b. ***Systemic Lupus Erythematosus (SLE) criteria:***
 - Confirmed diagnosis of SLE according to the Systemic Lupus International Collaborating Clinics (SLICC) Classification Criteria (See [Appendix 5](#)) at Screening, with symptom duration at least 6 months prior to Screening visit.
 - Positive antinuclear antibody (ANA) titer $\geq 1:80$ AND/OR positive anti-double-stranded deoxyribonucleic acid (anti-dsDNA) AND/OR anti-Smith antibodies at Screening.

4.2. Exclusion Criteria

Subjects with any of the following characteristics/conditions will not be included in the study:

1. Investigator site staff members directly involved in the conduct of the study and their family members, site staff members otherwise supervised by the investigator, or subjects who are Pfizer employees, including their family members, directly involved in the conduct of the study.
2. Participation in other studies involving investigational drug(s) within 30 days or 5 half-lives (whichever is longer) prior to study entry and/or during study participation. For investigational biologics, 5 half-lives or 180 days preceding the first dose of the investigational product (whichever is longer). If subjects participated in studies involving investigational biologics, which are biosimilars, the timeframe from previous use described in [Appendix 2](#) will apply instead.
3. Other acute or chronic medical or psychiatric condition including recent (within the past year) or active suicidal ideation or behavior or laboratory abnormality that may increase the risk associated with study participation or investigational product administration or may interfere with the interpretation of study results and, in the judgment of the investigator, would make the subject inappropriate for entry into this study.
4. Subjects with DAS28 score >5.1 can be enrolled only after consultation with the sponsor medical monitor.
5. Subjects with Clinical SLEDAI-2K score >8 can be enrolled only after consultation with the sponsor medical monitor.
6. Active central nervous system (CNS) manifestations, systemic vasculitis or pleuro/pericarditis which, in the opinion of the investigator or sponsor, is uncontrolled within 2 months of the Screening visit or leading to the incapacity of the subject to comply with consent and protocol requirements.
7. Active lupus nephritis, as defined by any of the following:
 - Proteinuria >1.5 g/24 hr or urinary protein to urinary creatinine ratio [Upr/Ucr] >2.0 at Screening; only one of these two tests is required at Screening.
 - Presence of red blood cell (RBC) casts or ≥ 10 RBC/hpf (in the absence of infection or menstrual hematuria at Screening);
 - Estimated Glomerular Filtration Rate (eGFR) $< 60 \text{ ml/min}/1.73 \text{ m}^2$ at Screening. The following formula will be used: $175 \times (\text{Serum creatinine})^{-1.154} \times (\text{Age})^{-0.203} \times (0.742 \text{ if female}) \times (1.212 \text{ if African-American})$;

- Requiring high-dose prednisone (greater than or equal to 40 mg/day) within 3 months prior to Screening;
- Requiring hemodialysis or cyclophosphamide (Cytoxin) within the 6 months prior to Screening.

8. Secondary antiphospholipid antibody syndrome (APS) associated with a thromboembolic event in 12 months prior to Screening and/or associated with any prior history of cerebro- or cardiovascular event due to APS.

9. Subject is taking or has taken prohibited medications (See [Appendix 2](#)), OR taking doses or formulations of medications not consistent with those allowed (See [Appendix 3](#)).

10. Presence of any other systemic rheumatic disease other than and not related to SLE/RA (Secondary Sjogren's syndrome is permitted).

11. Baseline chronic co-morbidities (other than SLE/RA) requiring systemic corticosteroid therapy (such as asthma or inflammatory bowel disease) starting 6 months prior to the Screening. Systemic is defined as oral, rectal, or any injectable route of administration (thus other routes are allowed, including inhaled, topical, ophthalmic, otic, and intranasal).

12. Subjects with any of the following infections or infections history:

- a. Active clinically significant viral, bacterial, or fungal infection, or any major episode of infection requiring prescription anti-infective treatment 2 weeks prior to Screening.
- b. History of recurrent infections defined as 3 or more of the same type of infection in a 12-month rolling period. This does not include vaginal candidiasis or onychomycosis provided these are considered by the investigator to be well controlled.
- c. Herpes infection meeting at least one of the following criteria:
 - A herpes zoster episode \leq 3 months prior to Screening;
 - History of recurrent (ie, more than one episode) herpes zoster;
 - History of a single episode of disseminated (multidermatomal) herpes zoster or herpes simplex.
- d. Positive human immunodeficiency virus (HIV) serological test at screening.
Note: a documented negative HIV test within 3 months of Screening visit is acceptable and does not need to be repeated at Screening.

- e. Evidence of active or latent infection of hepatitis B or hepatitis C based on screening tests (See [Section 7.1.9](#)). Subjects who are positive for hepatitis C virus antibody (HCV Ab) will be reflex-tested for hepatitis C virus ribonucleic acid (HCV RNA) and only if HCV RNA is negative, they may be considered for enrolled in this study.
- f. Current or past history of either 1) active tuberculosis (TB) infection or 2) latent TB that was inadequately treated or where adequate treatment cannot be documented.
- g. Clinically significantly abnormal chest X-ray per investigator opinion or evidence of active TB on chest X-ray. Subjects who had chest X-ray performed within 3 months prior to the Screening visit do not have to have chest X-ray performed, provided documentation is available.

13. Known hypersensitivity, intolerance or allergic reaction to the IP or placebo or any of its excipients, or history of severe hypersensitivity to monoclonal antibodies.
14. Known hypersensitivity or allergic reaction to pre- or post-infusion medications (corticosteroids, acetaminophen and antihistamines).
15. Known hypersensitivity or allergic reaction to Td or Trumenba vaccination.
16. Received any live virus or live-attenuated vaccines within 4 weeks prior to Screening, or expected during the study period (from Screening to subject's last visit).
17. Received plasmapheresis within 12 weeks prior to Screening or expected during the study period (from Screening to subject's last visit).
18. History of or planned organ transplant for the duration of the study (from Screening to subject's last visit).
19. Major surgery requiring use of general anesthesia within 6 weeks prior to Screening or planned or expected major surgery during the study period (from Screening to subject's last visit).
20. History of any malignancy within past 5 years prior to Screening (except adequately treated and removed basal and squamous cell carcinomas of the skin, and in situ cervical cancer intraepithelial neoplasia of the uterine cervix).
21. Subject abused drugs or consumed an excessive amount of alcohol in the past 12 months, based on the opinion of the investigator.
22. Presence of any of the following laboratory abnormalities at Screening:
 - B-cell count at Screening below the lower limit of normal (LLN), defined as 80 cells/ μ l (obtained from CLIA certified central lab).

- Total serum IgG <5 mg/dl (or 5 g/l).
- Hemoglobin <10 g/dL (100 g/L).
- White blood cell count <2.5 x 10⁹ /L (<2,500/mm³).
- Platelet count <75 x 10⁹/L per central laboratory results (75,000/mm³).
- Neutrophil count <1.5 x 10⁹/L (<1,500/mm³).
- Aspartate aminotransferase (AST) **or** alanine aminotransferase (ALT) level $\geq 2.0 \times$ upper limit of normal (ULN).
- Total bilirubin level $\geq 2.0 \times$ ULN; subjects with a history of Gilbert's syndrome may have direct bilirubin measured and would be eligible for this study provided the direct bilirubin level is \leq ULN.

Any abnormal results may be confirmed by a single repeat test, if deemed necessary by the investigator and approved by the sponsor medical monitor.

23. Pregnant female subjects; breastfeeding female subjects; fertile male subjects and female subjects of childbearing potential who are unwilling or unable to use one highly effective method of contraception as outlined in this protocol for the duration of the study and for at least three months after the last dose of investigational product.
24. Blood donation (excluding plasma donations) of approximately 1 pint (500 mL) or more within 60 days prior to dosing.
25. Unwilling or unable to comply with the criteria in the Lifestyle Requirements section of this protocol.

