- o. Serum FSH will be performed to confirm postmenopausal status for females who have been amenorrheic for at least 12 consecutive months. If post-menopausal for ≥ 5 years, it is at the investigator's discretion whether to confirm post-menopausal status by FSH.
- p. Serum pregnancy test will be conducted at a central lab. Urine pregnancy test will be conducted locally. For female subjects of childbearing potential, 2 negative pregnancy tests are required prior to receiving IP on Day 1 (1 negative serum pregnancy test at Screening and 1 negative urine pregnancy test on Day 1). Results of serum pregnancy test on Day 1 are not required prior to dosing.
- q. Includes hepatitis B surface antigen (HepBsAg), hepatitis B core antibody (HepBcAb) and hepatitis C antibody (HCVAb). Only subjects who are positive for HCV Ab will be reflex-tested for hepatitis C virus ribonucleic acid (HCV RNA).
- r. Includes testing for cytomegalovirus (CMV), Epstein Barr virus (EBV), herpes simplex virus type 1 (HSV-1), herpes simplex virus type 2 (HSV-2) and varicella zoster virus (VZV). Additional samples for viral surveillance sample may be taken at the time of an adverse event, as clinically appropriate.
- s. Includes total Ig, IgA, IgG, IgE and IgM.

C

C

- u. At dosing visits, PK samples will be collected preferably after vital signs and ECG, and within approximately 1 hour prior to dosing and at the end of infusion. If end of infusion is within 10 minutes of a scheduled PK sample, then only the scheduled sample will be collected.
- v. Includes anti-drug antibodies (ADA) and neutralizing antibodies (NAb). During dosing visits, samples to assess ADA and NAb will be collected prior to investigational drug administration.

C

C

C

C

- z. Approximately 1 hour prior to the administration of IP, each subject will be pre-treated with 1000 mg of oral acetaminophen, and an oral antihistamine (eg, 25 mg of oral diphenhydramine).

- aa. The total infusion time will be 120 minutes ± 10 minutes, unless a different time is needed to manage symptoms typical of infusion reactions. In such a case, the entire duration of study drug infusion should not exceed approximately 4 hours unless a different time is communicated to the site by the sponsor.

CCI

- cc. Please see [Section 7.1.10](#) for details.
- dd. Please see [Section 7.1.11](#) for details.

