Studies with other B cell depleting agents indicate the potential for viral and non-viral infections with PF-06835375, including severe cases resulting in death. Multiple agents that deplete B cells have been approved in both oncology and non-oncology indications (including rituximab, ocrelizumab, obinutuzumab and ofatumumab) and all carry label warnings for infections. Progressive multifocal leukoencephalopathy (PML) resulting in death has occurred with B cell depleting agents (most notably rituximab given the extensive use in multiple diseases), and has also been observed in SLE and RA subjects receiving immunosuppressive agents. Investigators should consider PML in any patient with new onset of or changes in pre-existing neurological signs or symptoms (See [Section 7.1.14](#)). The role of the Tfh subset of T cells in human immunity has yet to be established, and may contribute to the effective control of acute and chronic pathogens. Although no serious or opportunistic infections were observed in pre-clinical toxicity studies in non-human primates, subjects will be closely monitored throughout the study for signs/symptoms of infections. While appropriate risk mitigation has been incorporated into the study, possible risks will be communicated to study participants in the informed consent document.

Cytopenias have been observed with other depleting antibodies, including neutropenia, thrombocytopenia and anemia. Subject blood counts will be closely monitored throughout the study, including both CXCR5-positive cells and other cell lineages.

The PD of PF-06835375 will be evaluated [CCI](#)

[CCI](#)

When adverse reactions to the [CCI](#) occur, they are generally mild in nature and last for one or two days only. Symptoms include erythema and swelling around the injection site, feelings of general malaise, headache, myalgia and fever, and can be managed with paracetamol. Severe reactions are extremely rare; subjects with concomitant illnesses and a personal history of an allergic reaction to the [CCI](#) vaccine will be excluded.

[CCI](#)

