2. STUDY OBJECTIVES AND ENDPOINTS

Primary Objective:	Primary Endpoints:

 To evaluate the safety and tolerability of single and multiple ascending intravenous (IV) and subcutaneous (SC) doses of PF-06835375 in subjects with SLE and RA. 	
 Incidence of dose limiting or treatment related adverse events (AEs). Incidence, severity and causal relationship of treatment emergent AEs (TEAEs) and withdrawals due to treatment emergent adverse events. Incidence of abnormal chemistry, hematology, and urinalysis laboratory findings through the end of study. Abnormal and clinically relevant changes in vital signs and electrocardiogram (ECG) parameters. Incidence of infections.
Secondary Objectives:	Secondary Endpoints:

 To evaluate the effect of PF-06835375 on depletion of circulating CXCR5 positive B cells and cTfh cells in subjects with SLE and RA. To characterize pharmacokinetics (PK) profile of PF-06835375 in subjects with SLE and RA. 	
 Change from baseline in the number of circulating CXCR5 positive B cells and cTfh cells on Day 29 single dose of PF-06835375 and at Week 8 following multiple doses of PF-06835375. Serum PF-06835375 PK parameters after single and multiple doses: 
 Single Ascending Dose Phase: C_{max}, T_{max}, AUC_{inf}, AUC_{last}. Multiple Ascending Dose Phase: 
 First Dose: C_{max}, T_{max}, AUC_{tau}. Multiple Dose: C_{max}, T_{max}, AUC_{last}, AUC_{tau}, C_{min} and observed accumulation ratio (R_{ac}), peak-to-trough ratio (PTR).

 To evaluate immunogenicity of PF-06835375 in subjects with SLE and RA. 	
 Incidence of development of anti-drug antibodies (ADAs)/neutralizing antibodies (Nabs).
CCI	

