4.3. Randomization Criteria

Subjects will be randomized into the study provided they have satisfied all subject eligibility criteria. Subjects will be randomized within each cohort to receive either PF-06835375 or placebo. Both SLE and RA subjects will be enrolled into this study. There are no requirements for a minimum number of RA or SLE subjects in each cohort.

In order to mitigate any unanticipated acute safety risks, sentinel dosing will be employed for this study as described in [Section 3.2](#).

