7.1.5. Medical History

Investigators should make all reasonable efforts to obtain an accurate and complete medical history and history of prior medication use when evaluating whether a subject is eligible for the study. The following will be collected at Screening: complete medical history, SLE/RA disease history (including disease duration, extent of disease, and prior treatments), cardiovascular disease history, venous thromboembolic event history, alcohol and tobacco use history.

If the status of a subject's medical history is in doubt or information pertaining to a critical variable is conflicting, every reasonable step to secure proper documentation of correct medical status should be attempted. Documentation of the medical and medication histories over the protocol defined time periods should be available for sponsor review during the source data verification process. Questions about prior medications or eligibility should be directed to the sponsor Clinician or Medical Monitor.

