5.7. Protocol Deviations

Participants who experience events that may affect their PK profile may be excluded from the PK analysis. At the discretion of the pharmacokineticist a concentration value may also be excluded if the deviation in sampling time is of sufficient concern or if the concentration is anomalous for any other reason.

A full list of protocol deviations will be compiled and reviewed to identify major and minor deviations prior to database closure.

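### Exclusion criterion 22 gives the serum IgG limit as 5 mg/dL and as 5 g/L, two figures that differ 100-fold

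*Protocol*

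**What the plan says.** Criterion 22 of Protocol Section 4.2 lists laboratory abnormalities at Screening, any one of which excludes a subject. The IgG entry is "Total serum IgG <5 mg/dl (or 5 g/l"). The next entry, also in two units, is "Hemoglobin <10 g/dL (100 g/L"). White cells, platelets and neutrophils follow, each given per litre and per mm³.

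The line is in use. The Schedule of Activities has a serum immunoglobulin sample at Screening in both parts, and its footnote states: "Includes total Ig, IgA, IgG, IgE and IgM". Section 4.3 then makes eligibility a condition of randomization: "Subjects will be randomized into the study provided they have satisfied all subject eligibility criteria". SAP Section 5.7.1 refers back to Protocol Sections 4.1 and 4.2 for the eligibility assessment, so this line is also the standard against which an eligibility deviation would be judged.

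**The concern.** A mg/dL figure and a g/L figure with the same numeral cannot be the same concentration. The line therefore carries two candidate limits, and neither document says which one applies.

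The criterion gives no rationale for an IgG limit, but treating it as safety-related is a fair inference. Protocol Section 1.6 warns: "Studies with other B cell depleting agents indicate the potential for viral and non-viral infections with PF-06835375". Section 2 lists "Incidence of infections" among the primary endpoints. Two sites could decide differently on the same Screening value, and the same enrolled subject could be counted as an eligibility deviation or not.

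Routine reporting may not show this. Protocol Section 9.6 treats Screening laboratory data used for eligibility as source data that need not be reported unless otherwise noted.

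**Working it through.** **Inputs.** All limits come from Protocol Section 4.2, criterion 22. Expected cohort sizes and cohorts used come from SAP Section 2.1, Table 1.

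**Step 1: convert the IgG figures.**
- mg/dL to g/L: multiply by 10 dL/L and divide by 1000 mg/g. 5 × 10 / 1000 = 0.05 g/L.
- g/L to mg/dL: multiply by 1000 mg/g and divide by 10 dL/L. 5 × 1000 / 10 = 500 mg/dL.
- Ratio: 500 / 5 = 100.

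The stated equivalence is not reproduced in either direction.

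**Step 2: apply the same check to the other two-unit limits.**

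| Limit | First figure | Converted | Bracketed figure | Agrees |
|---|---|---|---|---|
| Hemoglobin | 10 g/dL | 10 × 10 = 100 g/L | 100 g/L | yes |
| White cells | 2.5 × 10⁹/L | 2.5 × 10⁹ / 10⁶ = 2,500/mm³ | 2,500/mm³ | yes |
| Platelets | 75 × 10⁹/L | 75 × 10⁹ / 10⁶ = 75,000/mm³ | 75,000/mm³ | yes |
| Neutrophils | 1.5 × 10⁹/L | 1.5 × 10⁹ / 10⁶ = 1,500/mm³ | 1,500/mm³ | yes |
| IgG | 5 mg/dL | 0.05 g/L | 5 g/L | no |

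Four of the five convert correctly. IgG is the exception.

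**Step 3: find which Screening values are affected.**
- Bracket read as a conversion: the limit is either 0.05 or 5 g/L. Below 0.05 g/L both figures exclude; at 5 g/L or above neither does. From 0.05 to below 5 g/L (5 to below 500 mg/dL) they disagree.
- Bracket read as below either figure: IgG <0.05 g/L or IgG <5 g/L is simply IgG <5 g/L. No value is decided two ways, and the mg/dL figure is redundant.

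**Step 4: check for downstream use.** The analysis sets in SAP Sections 5.1 to 5.4 rest on randomization or enrollment, dosing and available data. None uses the IgG limit. Protocol Section 9.1 says the sample size has no statistical basis, so that is untouched as well.

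**Step 5: size of the search.** SAP Table 1 shows 11 cohorts used. A1–A4: 4 × 4 = 16. A5–A6: 2 × 8 = 16. B1–B5: 5 × 8 = 40. Total 16 + 16 + 40 = 72, if each enrolled its expected number. Cross-check from the planned total: 112 − 16 (A7, A8) − 24 (X6) = 72. This is how many records to look through, not how many subjects are affected.

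**The case against.** The best defence is the wording itself. The IgG line is the only two-unit line in the criterion that contains the word *or*. Taken literally, it yields one operative limit and no conflicting decisions. That reading is possible, but it leaves the first-stated figure without effect, runs against the pattern of the neighbouring lines, and is nowhere stated to be the intended one.

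Safeguards also exist. Exclusion 3 lets the investigator exclude for a laboratory abnormality that raises risk. Criterion 22 allows one confirmatory repeat test, with the medical monitor's approval. Section 7.1.5 says: "Questions about prior medications or eligibility should be directed to the sponsor Clinician or Medical Monitor". Section 6.1 requires sponsor approval to screen and dose each subject, although its stated purpose is sentinel dosing and the number screened, not an eligibility check. These lower the chance of unnoticed entry. None says which figure applies.

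It is also fair to say that no harm is shown. The documents do not establish that any site applied the mg/dL figure, the laboratory manual is not available here, and the affected number may be zero. The SAP already reports actual doses and unused cohorts, so much or all of the enrollment may be over. This limits the weight of the point and makes the remedy largely retrospective. It does not make the two figures agree.

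Finally, the SAP plans a deviation review: "A full list of protocol deviations will be compiled and reviewed to identify major and minor deviations prior to database closure". Section 5.7.2 adds a discretionary decision on significant deviations for each analysis population. That review can classify a subject in the disputed range only once the limit is settled.

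**Conclusion.** The concern holds: the IgG limit is wrong as written, because its two figures differ by a factor of 100 and nothing else in the visible documents settles which is meant.

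The practical conflict depends on reading the bracket as a conversion, which the neighbouring lines support. Under that reading the disputed range is 0.05 to below 5 g/L; under the literal reading it is empty. The number of subjects in the range is not given. The effect is confined to eligibility decisions and deviation classification: no analysis set, sample size or planned method uses the limit. SAP Section 5.7.2 leaves room for judgment on significant deviations, but nothing there is tied to IgG.

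The line reads cleanly and is not redacted. A text-extraction fault cannot be wholly excluded, but nothing points to one. The point should be fixed because it concerns an operative, safety-relevant entry threshold and is cheap to settle.

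**What to change.** The sponsor should reconcile the two figures into a single IgG limit with consistent units, and record in a clarification memo which limit the laboratory and the sites actually applied. This review takes no position on which figure is correct.

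Before database closure, list every randomized subject with a Screening IgG of at least 0.05 and below 5 g/L, and classify each against the confirmed limit as part of the deviation review already planned. If the list is empty, the memo should say so, and the matter is closed.

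The cost is one memo and one filtered listing over about 72 subjects, on the enrollment assumption above. No analysis method changes.
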